6.4.4 Validating the iCHEC paediatric bleeding assessment tool in children with haemophilia

Primary objective: to describe the bleeding scores as assessed by a newly developed Paediatric
Bleeding Assessment Tool (iCHEC), in all paediatric patients with haemophilia, and in subgroups
according to haemophilia severity, age and treatment regimen (prophylaxis/on demand).
Determinants: Haemophilia severity, age, treatment regimen.
Population: All paediatric patients with haemophilia.

Endpoint: bleeding scores as assessed by a newly developed Paediatric Bleeding Assessment Tool. **Statistical analysis:** We will use descriptive statistics where appropriate.

6.5 Studies assessing immunological mechanisms that may lead to inhibitor formation in patients with haemophilia A

6.5.1 Assessing the relationship between FVIII-specific non-neutralizing antibodies and inhibitor formation:

Primary objective 1: To assess the prevalence of FVIII-specific non-neutralizing antibodies (NNAs) among non-inhibitor patients with severe, moderate and mild haemophilia A in the Netherlands.
Study design and population: A cross-sectional study design will be used. The population will consist of all haemophilia A patients without current inhibitors in the Netherlands.

Determinant: Disease severity (mild, moderate and severe) will be used as the determinant. **Endpoint:** The prevalence of non-neutralizing antibodies among non-inhibitor patients with haemophilia A in the Netherlands will be used as the endpoint. The Bethesda assay will be used to assess inhibitor presence. If negative, the presence and characteristics of NNAs will be assessed using an ELISA platform developed by Whelan et al. [70]

Statistical analysis: 95% confidence intervals for the prevalence (which is a binomial proportion) will be calculated by using the exact Clopper-Pearson method.

Primary objective 2: To characterize all FVIII-specific antibodies with respect to Ig class, IgG subclass and affinity, and to evaluate whether some of these characteristics are more associated with having neutralizing antibodies (inhibitors) rather than non-neutralizing antibodies (NNAs).

Study design and population: A cross-sectional study design will be used. The population will consist of all haemophilia A patients with neutralizing FVIII-specific antibodies(inhibitors) or non-neutralizing FVIII-specific antibodies (NNAs). Patients without any FVIII-specific antibodies will be excluded from

HiN-6 study

this analysis.

Determinant: The presence of non-neutralizing antibodies (NNAs) or neutralizing antibodies (inhibitors) will be used as the determinant. The presence of NNAs will be assessed using an ELISA platform developed by Whelan et al. [70] The Bethesda assay will be used to assess inhibitor presence.

Potential confounders: We will potentially adjust for FVIII genotype and family history of haemophilia/inhibitors as well as other potential genetic determinants such as HLA, IL-10, TNFα, CTLA4, HO-1 and FcgR gene polymorphisms.

Endpoint: Ig class, IgG subclass and affinity will be used as endpoints. The presence and characteristics of NNAs will be assessed using an ELISA platform developed by Whelan et al. [70]
Statistical analysis: The relationship between Ig class, IgG subclass, affinity and the presence of inhibitors or NNAs will be assessed using regression based methods.

Secondary objective 1: To assess whether F8 genotype and polymorphisms in immune response genes influence the development of non-neutralizing antibodies (NNAs).

Study design and population: A cross-sectional study design will be used. The population will consist of all haemophilia A patients with non-neutralizing FVIII-specific antibodies (NNAs) and all haemophilia A patients without any antibodies. Haemophilia A patients with neutralizing antibodies (inhibitors) are excluded from this analysis.

Determinants: FVIII genotype and family history of haemophilia/inhibitors as well as other potential genetic determinants such as HLA, IL-10, $TNF\alpha$, CTLA4, HO-1 and FcgR gene polymorphisms.

Potential confounders: See determinants

Endpoint: The presence or absence of non-neutralizing antibodies (NNAs) will be used as the endpoint.

Statistical analysis: The relationship between the determinants and the presence or absence of nonneutralizing antibodies will be explored using logistic regression.

Secondary objective 2: To assess whether F8 genotype and polymorphisms in immune response genes influence the development of either neutralizing antibodies (inhibitors) or non-neutralizing antibodies (NNAs).

Study design and population: A cross-sectional study design will be used. The population will consist of all haemophilia A patients with neutralizing FVIII-specific antibodies (inhibitors) or non-neutralizing FVIII-specific antibodies (NNAs). Patients without any FVIII-specific antibodies are excluded from this analysis.

Determinants: FVIII genotype and family history of haemophilia/inhibitors as well as other potential genetic determinants such as HLA, IL-10, TNF α , CTLA4, HO-1 and FcgR gene polymorphisms. **Potential confounders:** See determinants

Endpoint: The presence of neutralizing FVIII-specific antibodies (inhibitors) or non-neutralizing FVIII-specific antibodies (NNAs) will be used as the endpoint.

Statistical analysis: The relationship between the determinants and the presence of neutralizing FVIII-specific antibodies (inhibitors) or non-neutralizing FVIII-specific antibodies (NNAs) will be explored using logistic regression.

Secondary objective 3: To evaluate the association between non-neutralizing antibodies (NNAs) and bleeding frequency in patients with severe haemophilia A.

Study design and population: A cross-sectional study design will be used. The population will consist of all haemophilia A patients with non-neutralizing FVIII-specific antibodies (NNAs) and all haemophilia A patients without any antibodies. Haemophilia A patients with neutralizing antibodies (inhibitors) are excluded from this analysis.

Determinants: The presence/absence and titre of non-neutralizing antibodies (NNAs) will be used as the determinants.

Potential confounders: We will potentially adjust for the severity of haemophilia, FVIII genotype as well as VWF antigen levels and/or VWF activity

Endpoints: The modified bleeding severity score developed by Schulman et al [97] will be used as the endpoint (see paragraph 5.1.3).

Statistical analysis: The relationship between the presence/absence of non-neutralizing antibodies (NNAs) and bleeding severity will be assessed using linear regression.

Secondary objective 4: To evaluate potential misclassification of low-titre inhibitors as (low/high-affinity) non-neutralizing antibodies in patients with haemophilia A.

Study design and population: A cross-sectional study design will be used. The population will consist of all haemophilia A patients with NNAs in the Netherlands.

Determinant: An ELISA will be used to assess the presence of (low/high- affinity) NNAs.

Endpoint: The low-titre inhibitor assay will be used to assess low-titre inhibitor presence.

Statistical analysis: This objective will firstly be explored using descriptive statistics.

Secondary objective 5: To evaluate the diagnostic performance of a modified FVIII ELISA for detection of FVIII-specific antibodies (inhibitors), using the Bethesda assay as the reference test.

Study design and population: A cross-sectional study design will be used. The population will consist of all haemophilia A patients in the Netherlands.

Determinant: A modified ELISA will be used to detect the presence of high-affinity IgG4 FVIII-specific antibodies.

Endpoint: The Bethesda assay will be used to assess inhibitor presence; a cut-off value of 0.6 BU will be used.

Statistical analysis: The Bethesda assay will be used as the reference test, the modified ELISA will be used as the index test. We will calculate sensitivity, specificity, (positive and negative) predictive values, (positive and negative) diagnostic odds ratios and their corresponding confidence intervals.

6.5.2 Assessing dendritic cell response and T-cell activation in the FVIII immune response:

Primary objective 1: To compare the expression of interleukin-2 and TGF-beta in monocyte-derived dendritic cells after stimulation with FVIII with and without danger signals (e.g. LPS) in patients with non-neutralizing FVIII-specific antibodies (NNAs) and patients without any current FVIII-specific non-neutralizing antibodies.

Study design and population: A case-control study design will be used. The cases will consist of 25 severe patients with NNAs that never underwent ITI. The controls will consist of 25 severe patients without any current NNAs that never underwent ITI. All haemophilia patients must have a F8 intron-22 inversion mutation. Haemophilia patients with current or previous inhibitors are excluded. **Determinant:** The expression of interleukin-2 and TGF-beta in monocyte-derived dendritic cells after stimulation with FVIII and LPS will be used as the determinant. We will isolate PBMC's from all patients, monocyte-derived dendritic cells will be cultured, we will then assess the cytokine response to FVIII/LPS using RNA sequencing.

Potential confounders: We will potentially adjust for the previous number of EDs to FVIII, FVIII genotype and family history of inhibitor formation as well as other potential genetic determinants such as HLA, IL-10, TNFα, CTLA4, HO-1 and FcgR gene polymorphisms.

Endpoint: The presence or absence of NNAs will be used as the endpoint (coded as a dichotomous variable). Firstly, The Bethesda assay will be used to assess inhibitor presence. If negative, an ELISA will be used to detect the presence of NNAs.

Statistical analysis: We will use logistic regression to evaluate the association between interleukin-2 and the presence of NNAs and the relationship between TGF-beta and the presence of NNAs. In addition, we will examine the combined effect of increased expression of interleukin-2 and TGF-beta on the presence of NNAs using logistic regression.

Primary objective 2: To compare the regulatory T- cell count, as a proportion of all CD4+ T-cells in patients with non-neutralizing FVIII-specific antibodies (NNAs) or patients without any current FVIII-specific antibodies.

Study design and population: A case-control study design will be used. The cases will consist of 25 severe patients with NNAs that never underwent ITI. The controls will consist of 25 severe patients without any current NNAs that never underwent ITI. All haemophilia patients must have a F8 intron-22 inversion mutation. Haemophilia patients with current or previous inhibitors are excluded. **Determinant:** T-regulatory cell count, as a proportion of all CD4+ T-cells will be used as the determinant. T-regulatory cell count will be assessed using both flow cytometry and a quantitative real-time PCR assay developed by Epiontis (Epiontis Treg assay).

Potential confounders: We will potentially adjust for the previous number of EDs to FVIII, FVIII genotype and family history of inhibitor formation as well as other potential genetic determinants such as HLA, IL-10, TNF α , CTLA4, HO-1 and FcgR gene polymorphisms.

Endpoint: The presence or absence of NNAs will be used as the endpoint. Firstly, The Bethesda assay will be used to assess inhibitor presence. If negative, an ELISA will be used to detect the presence of NNAs.

Statistical analysis: We will use logistic regression to evaluate the association between the dendritic cell cytokine response and the presence/absence of NNAs

Chapter 7 - Ethical considerations

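### Section 6.5.1: the two genetic objectives ask who develops antibodies but classify patients by present status, so former inhibitor patients are misplaced

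*Protocol*

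**What the plan says.** Primary objective 1 of section 6.5.1 estimates NNA prevalence in "all haemophilia A patients without current inhibitors in the Netherlands". Status is assigned in two steps: "The Bethesda assay will be used to assess inhibitor presence. If negative, the presence and characteristics of NNAs will be assessed" by ELISA. Section 5.1.2 sets the Bethesda threshold at 0.6 Bethesda Units.

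Secondary objective 1 relates F8 genotype and immune-gene variants to the development of NNAs, comparing NNA patients with antibody-free patients. Its exclusion reads: "Haemophilia A patients with neutralizing antibodies (inhibitors) are excluded from this analysis". Secondary objective 2 asks whether the same genetic factors "influence the development of either neutralizing antibodies (inhibitors) or non-neutralizing antibodies (NNAs". It excludes patients without any antibody and states: "The presence of neutralizing FVIII-specific antibodies (inhibitors) or non-neutralizing FVIII-specific antibodies (NNAs) will be used as the endpoint".

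The only history listed among determinants or confounders in 6.5.1 is family history. Primary objective 2, for example, says: "We will potentially adjust for FVIII genotype and family history of haemophilia/inhibitors". The patient's own past inhibitor and past ITI do not appear as an exclusion, stratum or covariate.

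Section 6.5.2 also compares NNA-positive with NNA-negative patients, and is stricter: "Haemophilia patients with current or previous inhibitors are excluded", and cases and controls must never have had ITI (for the controls: "The controls will consist of 25 severe patients without any current NNAs that never underwent ITI").

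**The concern.** Developing an inhibitor is an event in a patient's past; a Bethesda result is his state today. The protocol gives reasons to expect the two to differ. Its abbreviation list defines ITI by the aim of eradicating inhibitors. Section 1.0 says that inhibitors mostly arise early in treatment and mainly affect very young patients, while section 4.1 recruits without an age limit. The case report form (CRF) has items for a first negative Bethesda assay, first normal recovery and relapse after successful ITI.

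If former inhibitor patients are sorted by present status alone, the genetic analyses mix two questions: which genotypes lead to an antibody, and which go with its persistence or disappearance. A genotype that raises inhibitor risk could then look like an NNA genotype, or a real difference between inhibitor and NNA patients could be diluted. Adjusting for genotype cannot repair this, because genotype is the exposure and the error lies in the outcome groups.

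**Working it through.** **Step 1. The protocol's own figure.** Section 4.4 gives 1800 × 0.70 = 1260 expected participants, which reproduces. It does not bear on this point. The protocol gives no number of former inhibitor patients, no NNA prevalence and no genotype frequency.

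**Step 2. Where each patient goes under 6.5.1 as written.**

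| History | Bethesda / ELISA in study | Secondary objective 1 | Secondary objective 2 |
|---|---|---|---|
| Never inhibitor | − / + | NNA case | NNA |
| Never inhibitor | − / − | control | excluded |
| Former inhibitor | − / + | NNA case | NNA |
| Former inhibitor | − / − | control | excluded |
| Current inhibitor | + | excluded | inhibitor |

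Rows 3 and 4 are treated exactly like rows 1 and 2, although those patients did develop an inhibitor. The word current appears only in primary objective 1. For the secondary objectives this reading follows from the Bethesda-then-ELISA classification and the silence on history.

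**Step 3. Illustration for secondary objective 1 (all inputs assumed).** Let f be the share of former inhibitor patients among Bethesda-negative patients. NNA prevalence is 10% in never-inhibitor patients and p in former inhibitor patients. The risk genotype is carried by 30% of never-inhibitor and 60% of former inhibitor patients, and is unrelated to NNA status within the former group. Pool the two 2×2 tables. For f = 10%, p = 30% and a true odds ratio (OR) of 1.0:

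- carriers with NNA: 0.9×0.3×0.1 + 0.1×0.6×0.3 = 0.045
- carriers without: 0.9×0.3×0.9 + 0.1×0.6×0.7 = 0.285
- non-carriers with NNA: 0.9×0.7×0.1 + 0.1×0.4×0.3 = 0.075
- non-carriers without: 0.9×0.7×0.9 + 0.1×0.4×0.7 = 0.595
- observed OR = (0.045×0.595)/(0.285×0.075) = 1.25

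Over f = 5–20% and p = 5–40%, a true OR of 1.0 is observed as 0.88 to 1.57, and a true OR of 2.0 as 1.58 to 2.22. The error can go either way.

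**Step 4. Illustration for secondary objective 2 (all inputs assumed).** The genotype is carried by 60% of current and former inhibitor patients and by 30% of never-inhibitor NNA patients. If a share m of the NNA group are former inhibitor patients, carriage in that group is g = 0.3(1−m) + 0.6m, and OR = (0.6/0.4)/(g/(1−g)).

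| m | g | OR |
|---|---|---|
| 0% | 0.30 | 3.50 |
| 10% | 0.33 | 3.05 |
| 20% | 0.36 | 2.67 |
| 30% | 0.39 | 2.35 |
| 50% | 0.45 | 1.83 |

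**Step 5. Primary objective 1 for comparison (assumed).** Observed prevalence = (1−f)×10% + f×p. With f = 2–20% and p = 5–40% it runs from 0.8×10% + 0.2×5% = 9.0% to 0.8×10% + 0.2×40% = 16.0%. With p = 10% nothing changes.

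**The case against.** Several points on the other side stand.

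- A reader might infer that all NNA substudies ignore past inhibitors. They do not: 6.5.2 excludes past inhibitors and ITI in both its objectives. The point concerns 6.5.1 only.
- A reader might infer that NNA prevalence in primary objective 1 is inflated. The population is stated openly, the design is cross-sectional, and a Bethesda-negative, ELISA-positive former inhibitor patient meets the protocol's operational definition of NNA. This is a coherent point prevalence of a mixed population. Nothing in the protocol says that residual antibody is commoner in former inhibitor patients, and step 5 shows that the figure can rise, fall or stay put.
- A reader might infer that most patients who ever developed an inhibitor fall outside the inhibitor arm of secondary objective 2. That needs the frequencies of ever and current inhibitor, and the protocol gives neither.
- Primary objective 2 compares antibody characteristics by present neutralizing status. History is not the classifier there, so the classification is sound.
- Section 6.5.2 is a 25-versus-25 mechanistic study in severe patients with one mutation. Its restriction does not bind a nationwide descriptive cohort; it shows only that the protocol recognises past inhibitors and ITI as relevant to an NNA comparison.

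It can also be said that the history is collected, that the secondary analyses are exploratory, and that coding may be left to an analysis plan. This limits the weight of the point but does not remove it: the protocol itself fixes the populations and endpoints of both genetic objectives, and as written they do not match a question about development.

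**Conclusion.** The concern holds for secondary objectives 1 and 2 of section 6.5.1. Both ask about antibody development and classify by present status, so former inhibitor patients are counted as NNA, counted as antibody-free, or dropped. The direction and size of the distortion cannot be derived from the protocol. The odds ratios above show only what is possible under assumed frequencies; with few former inhibitor patients the effect would be small. The two primary objectives of 6.5.1 are not invalidated. This is a cheap and worthwhile correction to two exploratory secondary analyses.

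**What to change.** In 6.5.1, define never, former and current inhibitor from CRF section 3 plus the study Bethesda result. Use the protocol's own relevance rule in the CRF instructions for items 3.4–3.16: two positive results, 1–4 weeks apart, at 0.6 BU/mL or higher. State how to handle the answer Unknown in item 3.1, historical results recorded against a local cut-off (item 3.4), and a single positive study sample, which cannot meet a two-occasion rule alone.

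- Secondary objective 1: exclude former as well as current inhibitor patients.
- Secondary objective 2: compare ever inhibitor with NNA in never-inhibitor patients, keep the current-status comparison as a sensitivity analysis, and note as a limitation that past NNAs are not recorded.
- Primary objective 1: keep the stated point prevalence and also report it separately for never-inhibitor and former inhibitor patients.
- Primary objective 2: keep the current-status classification and flag former inhibitor patients.

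No new data are needed. The cost is fewer NNA cases and controls in the genetic analyses, plus the work of writing the rules for unknown histories and local cut-offs.

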- To characterize all FVIII-specific antibodies with respect to Ig class, IgG subclass and affinity, and to evaluate whether some of these characteristics are more associated with having neutralizing antibodies (inhibitors) rather than non-neutralizing antibodies (NNAs).

Secondary objectives:

- 1. To assess whether F8 genotype and polymorphisms in immune response genes influence the development of non-neutralizing antibodies (NNAs).
- To assess whether F8 genotype and polymorphisms in immune response genes influence the development of either neutralizing antibodies (inhibitors) or non-neutralizing antibodies (NNAs).
- 3. To evaluate the association between non-neutralizing antibodies (NNAs) and bleeding frequency in patients with severe haemophilia A.
- 4. To evaluate potential misclassification of low-titre inhibitors as non-neutralizing antibodies

in patients with haemophilia A.

5. To evaluate the diagnostic performance of a modified FVIII ELISA for detection of FVIIIspecific antibodies (inhibitors), using the Bethesda assay as the reference test.

2.5.2 Specific objectives assessing dendritic cell response and T-cell activation in the FVIII immune response:

Primary objectives:

[figure not shown]
- To compare the expression of interleukin-2 and TGF-beta in monocyte-derived dendritic cells after stimulation with FVIII with and without danger signals (e.g. LPS) in patients with nonneutralizing FVIII-specific antibodies (NNAs) and patients without any current FVIII-specific non-neutralizing antibodies.
- To compare the regulatory T- cell count, as a proportion of all CD4+ T-cells in patients with non-neutralizing FVIII-specific antibodies (NNAs) or patients without any current FVIIIspecific antibodies.

Chapter 3 - Study design

HiN-6 study design

The HiN-6 study will consist of both cross-sectional and longitudinal observational studies, according to the specific research objective. A mixed-methods approach will be used for data collection and analysis. All participants will be asked to fill out a questionnaire and to provide a blood and urine sample. In addition, information will be obtained from medical records. For some of the planned substudies, a smaller number of patients will be asked to provide an additional blood sample at a second visit. Detailed study procedures can be found in chapter 5.

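### Section 6.5.1, secondary objective 2 asks whether genes influence antibody development but analyses only antibody-positive patients, so at best it compares antibody types

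*Protocol*

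**What the plan says.** Protocol 2.5.1 and 6.5.1 give secondary objective 2 in the same terms: whether F8 genotype and polymorphisms "influence the development of either neutralizing antibodies (inhibitors) or non-neutralizing antibodies (NNAs").

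Section 6.5.1 then fixes the rest of the analysis:
- **Population:** haemophilia A patients with an inhibitor or an NNA. "Patients without any FVIII-specific antibodies are excluded from this analysis".
- **Endpoint:** "The presence of neutralizing FVIII-specific antibodies (inhibitors) or non-neutralizing FVIII-specific antibodies (NNAs) will be used as the endpoint".
- **Model:** the relationship "will be explored using logistic regression".

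Two neighbouring objectives in 6.5.1 matter:
- **Secondary objective 1** also asks about influence on development, here of NNAs. It compares patients with NNAs with antibody-free patients: "Haemophilia A patients with neutralizing antibodies (inhibitors) are excluded from this analysis".
- **Primary objective 2** uses the same antibody-positive population as secondary objective 2, but its question is openly about type: which antibody characteristics are "more associated with having neutralizing antibodies (inhibitors) rather than non-neutralizing antibodies (NNAs").

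**The concern.** Whether a gene influences development of an antibody is a question about patients who have it against patients who do not. Once the antibody-free patients are removed, that comparison is gone. What remains is either an endpoint without variation or a comparison of one antibody type with the other.

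The second has a different null hypothesis: that genotype does not distinguish the types among antibody-positive patients. A null result could be reported as no genetic influence when the variant raises both risks. A variant that raises only NNA risk could be reported as protecting against inhibitors.

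This is not a detail left to a statistical analysis plan. The protocol itself fixes population, endpoint and model, and they do not match the objective.

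**Working it through.** The protocol gives no sample size, prevalence or effect size for this objective, so there is no figure to reproduce. The main result is algebraic. The power figures rest on assumptions, labelled below.

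**1. Literal reading.** In the planned set, P(inhibitor or NNA) = 1 for every patient. The outcome is constant and logistic regression cannot be fitted.

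**2. Inhibitor versus NNA.** Let pᵢ and pₙ be the risks of inhibitor and NNA in non-carriers, and RRᵢ and RRₙ the relative effects of a variant. Among antibody-positive patients:

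OR = (RRᵢ·pᵢ / RRₙ·pₙ) / (pᵢ / pₙ) = RRᵢ / RRₙ

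If RRᵢ = RRₙ, the OR is 1 whatever the prevalence or sample size. The same holds if the two odds ratios against antibody-free patients are equal.

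**3. Worked values, assuming pᵢ = 5% and pₙ = 20%:**

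| Effect of variant | Inhibitor vs NNA (planned) | Any antibody vs none |
|---|---|---|
| RRᵢ 1.5, RRₙ 1.5 | 1.00 | 1.80 |
| RRᵢ 2, RRₙ 2 | 1.00 | 3.00 |
| RRᵢ 2, RRₙ 1 | 2.00 | 1.29 |
| RRᵢ 1, RRₙ 2 | 0.50 | 2.45 |
| RRᵢ 1.5, RRₙ 2 | 0.75 | 2.71 |
| +5 points on each risk | 1.60 | 1.62 |

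First row in full: carriers have 7.5% inhibitors, 30% NNAs and 62.5% neither. Planned OR = (7.5/30)/(5/20) = 1.00. Any versus none = (37.5/62.5)/(25/75) = 1.80. In the fifth row the variant raises both risks, yet the planned OR is below 1. The last row shows that equal must mean equal in relative terms: equal absolute rises do move the planned OR.

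**4. Rejection rates by simulation.** Assumed: 20% carriers; 5% inhibitors and 15–30% NNAs in non-carriers; 600–1000 haemophilia A patients; 5% chi-square tests; variant with an odds ratio of 2 on both types.
- Inhibitor vs NNA (secondary objective 2 as planned): about 5%.
- NNA vs none (secondary objective 1 as planned): about 78–99%.
- Any antibody vs none (not planned): about 86–99%.
- Inhibitor vs none (not planned): about 40–60%.

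**5. Other analyses that might cover inhibitor versus antibody-free.**
- Secondary objective 1 excludes inhibitor patients.
- Primary objective 2 is confined to antibody-positive patients and treats genes as possible confounders.
- Secondary objective 5 is a diagnostic comparison of assays.
- Both case-control studies in 6.5.2 exclude current or previous inhibitors.
- Section 6.1.1 describes inhibitor formation by severity and calendar time.

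None reports a genetic contrast of inhibitor patients with antibody-free patients.

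**6. Who is in the antibody-free group.** Secondary objectives 1 and 2 classify patients by cross-sectional antibody status and do not exclude past inhibitors, whereas 6.5.2 explicitly does. A patient whose inhibitor has disappeared would therefore count as antibody-free or NNA. Section 3.0 of the case report form (Appendix 1) records current or previous positive Bethesda assays and immune tolerance induction, so these patients can be identified.

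**The case against.** The strongest defence is that the population is deliberate and only the objective is loosely worded. Section 6.5.1 is about how NNAs relate to inhibitors, primary objective 2 uses the same population, and the two secondary objectives can be read as steps: NNA versus none, then inhibitor versus NNA. A two-level outcome suits logistic regression. This is plausible, and on that reading population and model can stand. The objective cannot: it uses the same development wording as secondary objective 1, where the reference is antibody-free patients.

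A reader might infer that a shared genetic effect would go undetected in the whole plan. The protocol does not support that. Secondary objective 1 tests the same variants on NNA versus none and would usually catch the NNA part, as step 4 shows.

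A reader might also infer that the effect on inhibitors cannot be recovered. That too goes too far. Log OR (inhibitor vs none) = log OR (inhibitor vs NNA) + log OR (NNA vs none), and the plan estimates both terms. The identity is exact for a single unadjusted factor. The contrast is derivable, but the protocol neither plans nor reports it.

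The reversed-sign risk arises only if inhibitor versus NNA is read as inhibitor versus none and secondary objective 1 is ignored. Finally, the algebra does not say how common variants with equal relative effects are.

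**Conclusion.** The mismatch between objective, population and endpoint is real and follows from the protocol's text alone. Within secondary objective 2, a variant with equal relative effects on both antibody types is invisible at any sample size; this needs no assumed input. The power figures do depend on assumed carrier frequency, prevalences and numbers, and serve only as illustration.

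The gap is limited to this analysis and to the unreported inhibitor-versus-none contrast. Severity is moderate: the objective is secondary and exploratory, no main endpoint or sample size depends on it, and it can be corrected without new data.

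**What to change.** In 6.5.1, secondary objective 2:
- Keep antibody-free haemophilia A patients as the reference group and fit one multinomial logistic model (none / NNA / inhibitor) on the listed determinants.
- Report inhibitor vs none and NNA vs none as the main contrasts. Add inhibitor vs NNA, labelled as antibody type among antibody-positive patients.
- Use the inhibitor history on the case report form to separate patients with past inhibitors from the none and NNA groups, or exclude them in a sensitivity analysis.
- Describe results as associations with antibody status, since status is current and cross-sectional.

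If the sponsor intended only inhibitor versus NNA, reword the objective in 2.5.1 and 6.5.1 to say so and define the endpoint as antibody type. That removes the contradiction but leaves inhibitor versus none unreported.

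The cost is a wording change and one different model. The antibody-free patients and the same determinants are already used in secondary objective 1, so no new patients or assays are needed. The inhibitor-versus-none contrast will have modest power if inhibitors are rare (about 40–60% at an odds ratio of 2 under the assumptions above), so confidence intervals should be reported.
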